Once randomized participants begin the intervention, data on treatment adherence will be monitored by research staff on an ongoing basis. Adherence will be measured as the number of times the participant consumes the placebo or ketone supplement. Adherence will be reviewed after every 5 participants or quarterly (whichever comes first) and if the safety officer has concerns about whether compliance has reached a level that might inhibit the ability of the study to test its primary hypotheses, he will suggest a conference call for study investigators to discuss methods for improving compliance.

Statistical analyses and stopping rules

Although no formal power analysis was conducted for this study (due to exploratory nature of the study as pilot and feasibility), our 2:1 (ketone:placebo) recruitment strategy will provide opportunity to detect smaller differences in the ketone treated group. We plan for no interim efficacy analyses and will not unblind until recruitment is complete. In this minimal-risk study, it is more likely that drop-outs or difficulty in recruiting adequate numbers of participants will require stopping the trial than that excess adverse events will occur and require stopping the trial. However, as outlined elsewhere, we will monitor adverse event rates in all participants and aggregate by randomized group. The safety officer, together with the PI, will alert the UAB IRB and the NIH if a larger than reasonably expected adverse event rate should occur in either treatment condition. Other issues relating to stopping rules for this trial include:

New Information

It is exceedingly unlikely that any new information will become available during this trial that would necessitate stopping the trial.

Limits of Assumptions

It is possible that baseline differences between the groups, excessive study dropouts, and/or missing data by the interim measurement time points will limit the value of data analysis of measurements. Baseline differences will be evaluated and effects on the power to detect differences in the primary outcome will be evaluated and communicated to the PIs, and safety office. Given the monitoring plans outlined elsewhere in this document as well as the randomized design of this study, it is exceedingly unlikely that there will be baseline differences between groups of any magnitude to threaten the validity of the study.

Limits of Rules

We acknowledge that there are other situations that could occur that might warrant stopping the trial and have a section in the safety report/checklist to identify other situations that might be of safety concern, which will allow for communication of concerns to the study MPIs, statistician, and safety officer.

Informed consent

After prospective participants have been preliminarily screened for eligibility and informed about the details of the study protocol, they will be asked to review the informed consent document. They will have the opportunity to ask questions and discuss all aspects of the study prior to providing consent. Informed consent will be obtained by the study coordinator or other designated research personnel with IRB clearance and appropriate training in the conduct of human research. It will be made clear that participation is voluntary and refusal to participate will not affect their eligibility or standing in other studies or programs at UAB nor will it affect the clinical care or other services they receive from their primary care physician.

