METHODS: Describe the procedures for all aspects of your protocol. Tell us what you are doing.

Participants will be recruited by the Principal Investigator or Study Coordinator from the inpatient and **outpatient** CF population at UAB. Following admission to UAB Hospital for a routine CF exacerbation, **or within the outpatient setting**, the Study Coordinator will discuss the study with participants and obtain written informed consent before initiating the study.

Patients will be randomly allocated in unbalanced numbers (2:1) (n = 15 ketone and n = 8 control) to receive a ketone monoester or an identical-tasting placebo, respectively, for 8 days during the course of hospitalization for treatment of acute pulmonary exacerbation (One, 60 mL bottle of either a ketone ester will be consumed twice daily (30 mL or 15.0 g per dose) (KE4, KetoneAid, Falls Church, VA; 15.0 g or placebo (PL, flavored to closely match taste of the ketone) will be administered following an overnight fast and again at 1500h.

Participants will be **asked to drink about 1 fluid ounce of the ketone or placebo supplement twice a day (once in the morning and once mid-late afternoon) for up to 7 days. Each day in the study, the participant will be asked to fast overnight for about 8 hours before drinking the first dose of ketone or placebo. Following administration of the first dose of either the ketone or placebo and on either day 5, 6, or 7 a small drop of blood will be obtained from their finger before (time 0 min) and 15, 30, 60, 90, and 120 min after drinking the supplement. On days in between visit 1 and visit 2, we will check their blood sugar before drinking the supplement and 30 minutes after they drink the supplement. We will use a commercially available ketone meter (Keto-Mojo, Napa, CA) that provides a rapid assessment of blood ketone and glucose (sugar) levels. The Keto-Mojo device requires a finger stick with a lancet, identical to those used to measure blood sugar, and uses only a small drop of blood. Patients will be educated on how to use the device and self measure ketone and blood sugar.**

Blood sampling will occur from their indwelling catheter or **venipuncture** at day 1 and at day 5, 6, or 7 before administration of the ketone or placebo. We will try to coordinate this with any blood sampling done for clinical care.

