The Keto-Mojo device requires a finger stick with a lancet, identical to those used to measure blood sugar, and uses only a small drop of blood. The device provides values within about 15 seconds following sampling. An alcohol prep will be used to cleanse the surface of the skin prior to each stick and a bandage will be applied to reduce risk of infection.

Participants will remain on all CF chronic care medications **and/or** standard exacerbation therapy (intravenous antibiotics and increased airway clearance throughout the course of the study. The study pharmacist will provide the ketone or placebo supplements by computer-generated random assignment in blocks of three participants and will have sole access to the randomization code.

Spirometry measurements, CRP, and, history/physical exam and Sputum bacteriology will be conducted at the beginning of hospitalization as part of standard of care (these results will be pulled from the medical record for study purposes. Spirometry measurements and history/physical exams will also be performed at the end of hospitalization as part of standard of care and will be pulled from the medical record for study purposes.

For outpatient subjects, these results will be pulled from the medical record and study procedures will also be performed at visit 1 and visit 2 as according to the consent

Spirometry will also be performed in addition to those for standard care just before the participant drinks the ketone supplement or placebo control and one hour after on day 1 and either day 5, 6 or 7.

Additional sputum and blood will be collected at baseline before the treatment and at patient-discharge for trial-specific readouts.

The participants will also be asked to complete the CFQR questionnaire and a food diary every night. They will also be asked to complete the symptom questionnaire on hour after receiving the morning ketone or placebo.

REQUIRED - SELECT ONE OR BOTH: Will this be a retrospective study and/or a prospective study?

Yes No * Retrospective

Yes No * Prospective

Yes No * Will the study involve the prospective collection or analysis of data, documents, or records?

Yes No * Will the study involve the prospective collection or analysis of biospecimens?

What is the expected end date of the study (including data analysis)?

* Provide the total number of subjects to be included at all sites, both retrospectively (including records) and prospectively.

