- Pregnant women or fetuses
- Prisoners
- Medical Residents
- Study Staff or investigators named on this application
- Students
- Others
- None of the above, not targeting specific populations

How will the study team identify potential subjects? Select all that apply.

- Non-UAB physicians Non targeted/unknown (e.g., chart review) Other

If chart reviews will be used to identify potential subjects that are not your own patients, request a partial waiver of HIPAA Authorization for the purpose of identifying individuals for recruitment.

Describe.

Participants will be recruited by the principal investigator or Study Coordinator from the inpatient CF population at UAB. [name] is a UAB physician and part of the UAB CF Care team. He is a Sub Investigator on this project and will assist in recruiting patients.

*Describe participant inclusion/exclusion criteria, including sex, race/ethnicity, age, and health status.

Inclusion criteria will include diagnosis of CF, age > 19 years, colonization with Pseudomonas Aeruginosa, and acute pulmonary exacerbation requiring inpatient care or out-patients .

Exclusion criteria include concurrent or recent (within 28 days of enrollment) use of corticosteroids, acute respiratory failure requiring the use of invasive or noninvasive ventilation, chronic liver or renal disease, and pregnancy

Describe the estimated time commitment of each subject. Examples: 1) One hour once a week for 52 consecutive weeks; 2) Twenty minutes to complete a one-time survey; 3) One interview lasting 60 minutes. Enter "N/A" if participants are not directly involved.

The participant involvement will include 2 visits over 7 days of data collection

Yes No * Will a Certificate of Confidentiality be obtained from the NIH?

What recruitment materials/methods will be used to recruit subjects. Select all that apply.

Flyer

Where will the flyer be distributed?

[UAB CF Clinic](#)

Internet post/blog/website

ResearchMatch

Subject pool/repository

Printed brochure

Letter to healthcare providers

Letter to potential subjects

Printed ad

Radio/TV ad

Email solicitations

Direct subject contact

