Yes No Are you requesting the IRB make a Nonsignificant Risk determination for this device?

Describe the plan for the storage, dispensing, and disposal of the device being studied. Note: If the device is not FDA-approved, the plan must include methods to segregate the investigational devices from other devices available for general use.

[The ketone meter is multi use and will be kept by the research coordinator, this device is not given out to patients](#)

Describe how safety will be monitored for this device.

[There is no safety monitoring for this device](#)

Refer to the following FDA guidances for helpful information and examples.

- 1) [Frequently Asked Questions About Medical Devices](#)
- 2) [Significant Risk and Nonsignificant Risk Medical Device Studies](#)
- 3) [In Vitro Diagnostic Device \(IVD\) Studies - Frequently Asked Questions](#)

University of Alabama at Birmingham

Office of the IRB

[contact] | [contact]

www.uab.edu/irb

Questions?

Form Version: 2.0 | Date: 01/04/2021

Drug Review Sheet

DRUG SELECTION

Drugs

Drug name [exogenous ketone ester](#)

Yes No Is an Investigational New Drug Application (IND) required?

Yes No Has the requirement for an IND been waived?

Yes No Has the drug received FDA Approval?

Provide the name of the person holding the IND.

[NA This a supplement and does not require FDA approval](#)

Submit a copy of the Release of Drugs for Human Research Use (UAB Pharmacy (FOR 217), Children's of Alabama (FOR 218).

From where will the drugs be obtained?

[A company called Ketone Aid will provide the blinded supplement or placebo. The inpatient participants will receive the ketone supplement and placebo from the pharmacy but the outpatient participants will receive the ketone supplement and placebo from the research staff.](#)

Yes No Do you have an investigator's brochure available?

Describe the plan for the storage, dispensing, and disposal of the drug(s)/biologic(s).

[For the outpatient participants, the PI will store, monitor and dispense the blinded product to the research staff for dispensing to the patient per the randomization code. The PI will maintain a product accountability log.](#)

[For the inpatient participants, the research pharmacy will store and dispense the supplement to the participant. The research pharmacy will maintain a product accountability log for the inpatients.](#)

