This randomized controlled trial (RCT) aims to evaluate the effectiveness of a commercially available ketone supplement on pulmonary function and markers of inflammation and metabolic health in patients with cystic fibrosis (CF) admitted for acute pulmonary exacerbation and a cohort of stable outpatient CF subjects. To accomplish this goal, a 5-7 day RCT will be conducted to compare the effects of ketone supplementation to a placebo control. The primary outcome will be differences in pulmonary function, namely FEV1.0, FVC, and FEV1.0/FVC. Secondary outcomes will include quantitative assessment of circulating insulin, glucose, and a number of inflammatory markers associated with the NLRP3 inflammasome. Qualitative assessment of tolerability and the feasibility of delivery will also be extensively examined. Compared to placebo control and standard care, we hypothesize that the ketone ester (KE4, KetoneAid, Falls Church, VA) will produce greater reductions in markers of inflammation and improvements in pulmonary function. We further hypothesize that ketone supplementation will be well-tolerated and prove to be feasible as it relates to administration and consumption of the ketone. Of note, this Ketone supplement is considered GRAS and does not require FDA IND or FDA oversight.

The intervention and measurement protocols pose minimal risk to participants (as described below). Because of this low-risk status, the data safety monitoring plan (DSMP) for this trial focuses on close oversight by Medical Monitor, [name]. We will also provide prompt reporting of excessive adverse events and any serious adverse events to the Cystic Fibrosis Center, IRB at the University of Alabama at Birmingham (UAB) and NIH. The data safety monitoring plan (DSMP) outlined below will adhere to the protocol approved by the UAB IRB.

Safety reports will be sent to the study statistician, the MPIs, and to medical oversight at the schedule specified below in the table. The project coordinator will be responsible for assembling the data and producing these reports, as well as assuring that all parties obtain copies of these reports. The frequency of data review for this study differs according to the type of data and can be summarized in the following table:

Data type	Frequency of review
Subject accrual (adherence to protocol regarding demographics, inclusion/exclusion)	After every 5 patients that complete the study

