Adverse event rates (e.g. gastrointestinal distress or dizziness)	As they occur (cumulative reports also reviewed quarterly)
Serious Adverse Events	Immediate reporting (within 24 hrs) to IRB
Compliance to treatment	After every 5 patients that complete the study

Qualifications and responsibilities of Medical/Safety Oversight

[name] will serve as medical monitor for this study. [name] is an Assistant Professor of Medicine at UAB. He has conducted numerous CF-related clinical trials and has extensive experience serving as a Co-Investigator for NIH-funded studies. As Medical Monitor, [name] will review the reports sent by the project coordinator (at the frequency outlined above) to determine whether there is any corrective action, trigger of an *ad hoc* review, or stopping rule violation that should be communicated to the study investigator, UAB IRB, and NIH.

Measurement and reporting of participant accrual, adherence to inclusion/exclusion

criteria and site performance Review of the rate of participant accrual and adherence to pre-specified inclusion/exclusion criteria will occur after the recruitment of every five patients throughout the study. During this phase, the target is to enroll approximately five patients per quarter. No specific subgroups will be tracked. We envision a high retention rate as this study will be conducted in an inpatient setting and will have close follow-up in the outpatient cohort. The quarterly review will assess this enrollment rate as well as to assure that participants meet eligibility criteria as outlined in the grant proposal. To accomplish this, the study statistician will oversee the preparation of data tables summarizing recruitment and enrollment status and demographic characteristics. In the event that participant accrual rates fall below projected levels, the study investigators will convene a conference call to discuss potential strategies to modify the recruitment, screening, and/or enrollment protocols for future recruitment efforts and will report any requested changes to the UAB IRB, medical/safety officer, and NIH.

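### The Methods have patients self-measure glucose between visits, but the device sheet keeps the same meter with the coordinator; if the sheet is followed, outpatients have no described way to take 6 to 10 readings each

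*Protocol*

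**What the plan says.** The Methods (Protocol, section 1) set two kinds of finger-stick measurement with the Keto-Mojo meter. On day 1, and again on day 5, 6 or 7, there is a profile "before (time 0 min) and 15, 30, 60, 90, and 120 min after drinking the supplement". In between, the Methods say: "On days in between visit 1 and visit 2, we will check their blood sugar before drinking the supplement and 30 minutes after" the dose. They continue: "Patients will be educated on how to use the device and self measure ketone and blood sugar".

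The Device Review Sheet for the same meter, in answer to the question on storage and dispensing, says: "The ketone meter is multi use and will be kept by the research coordinator, this device is not given out to patients".

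The trial enrols inpatients and, in the words of the data safety monitoring plan (Appendix 9), "a cohort of stable outpatient CF subjects". For outpatients the Methods say that "study procedures will also be performed at visit 1 and visit 2 as according to the consent". Section 9 gives the time commitment: "The participant involvement will include 2 visits over 7 days of data collection". Appendix 9 adds that the study "will have close follow-up in the outpatient cohort", in a sentence about retention that mentions no measurement.

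**The concern.** The two instructions concern one device and point in opposite directions. For an inpatient the conflict does little harm, because the coordinator can bring the meter to the bedside. An outpatient has two visits, and dosing is twice daily for up to 7 days, so most doses are taken away from the site. A coordinator who follows the device sheet leaves that participant without the instrument the Methods rely on. If the Methods mean that staff take the readings, the document describes no outpatient contact at which they would do so.

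A likely cause, which is an inference, is that the extension to outpatients reached some forms and not others. The Drug Review Sheet has a separate supply route for outpatients; the Device Review Sheet has none.

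At stake is the only glucose measurement described between visits. Appendix 9 says that exogenous ketones stimulate insulin secretion and mildly lower glucose, and the morning dose follows an overnight fast of about 8 hours. Without these readings, a fall in glucose that causes no symptoms on those days would go unseen in outpatients. Daily adverse event collection continues, but it depends on symptoms.

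**Working it through.** The Protocol states no total for these readings, so there is no figure to reproduce. The count is direct.

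**Inputs**
- Visit 1 is taken as day 1 and visit 2 as day *d* = 5, 6 or 7 (Methods, section 1).
- Readings per checked dose: 2, one before and one 30 minutes after (Methods).
- Checked doses per day: not stated. The Methods refer to the supplement without naming the morning or the afternoon dose. One is assumed; two is shown as the alternative.
- Visit-day readings: 6 time points (0, 15, 30, 60, 90 and 120 minutes) at 2 visits, so 6 × 2 = 12 (Methods; data sheet, Appendix 2).

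**Formulas**
- Days strictly between visits = *d* − 2.
- Between-visit readings = 2 × *c* × (*d* − 2), where *c* is the number of checked doses per day.
- Share of planned finger-stick glucose readings = between-visit readings ÷ (between-visit readings + 12).

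**Results per outpatient**

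| Visit 2 | Days between | One dose checked | Share | Both doses checked | Share |
|---|---|---|---|---|---|
| Day 5 | 3 | 6 | 6/18 = 33% | 12 | 12/24 = 50% |
| Day 6 | 4 | 8 | 8/20 = 40% | 16 | 16/28 = 57% |
| Day 7 | 5 | 10 | 10/22 = 45% | 20 | 20/32 = 62.5% |

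The shares describe planned finger-stick readings, not information on any endpoint. The document does not give the number of outpatients. With 15 + 8 = 23 participants in all, it lies between 0 and 23, so no trial total can be stated.

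**Can the visible text be reconciled for outpatients?**
- Self-measurement needs the meter in the patient's hands; the device sheet rules that out.
- Staff measurement needs a contact between visits; section 9 gives two visits, and the Methods place outpatient procedures at those two.
- The promised close outpatient follow-up is not said to include a meter or a reading.
- The consent form might settle the matter. The Methods defer to it for outpatient procedures, but it is not among the pages available for review.

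**The case against.** The strongest case on the other side has four parts.

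1. **The Methods may prevail.** They are the operative procedure, while the device sheet answers one administrative question. Section 9 describes data collection over 7 days, and the Methods already ask participants to complete a food diary and questionnaires daily. Staff may simply hand out meters. This stands: a reader might infer that outpatient readings will be missing, but the document shows only conflicting instructions, and the loss follows only if the device sheet is obeyed.

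2. **The consent form may resolve it.** This also stands, as a limit on what can be concluded.

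3. **No endpoint depends on these readings.** Appendix 9 lists circulating glucose as a secondary outcome, so a reader might infer that this outcome is compromised in outpatients. The text does not say which readings it uses, and the blood draws at the two visits would fit equally well. The stronger reading is not supported.

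4. **The safety value is modest.** Appendix 9 expects no more than a 5–7% fall and acts on symptomatic hypoglycemia; no glucose threshold is set. A reader might infer that safety monitoring fails. It does not: the profiles at both visits, daily adverse event collection and close follow-up remain. What is lost is detection of a symptom-free fall on the days between.

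A reader might also see a second contradiction, because section 26 names only gastrointestinal effects while Appendix 9 names glucose lowering. Section 26 presents its list as what the side effects include, not as complete, and Appendix 9 is attached to the same submission. That does not add to the point.

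None of this removes the conflict. Two incompatible instructions for one meter remain in force, and nothing visible says which applies to outpatients.

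**Conclusion.** The point holds as a contradiction in device custody with a limited consequence. If the device sheet is followed, and unless the consent form provides otherwise, an outpatient has no described way to take 6, 8 or 10 planned glucose readings (visit 2 on day 5, 6 or 7, one checked dose a day), or 12, 16 or 20 if both doses are checked. This assumes that visit 1 is day 1 and that no undocumented meter or staff contact is arranged.

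The effect is confined to between-visit glucose monitoring in outpatients. The primary spirometry outcome, the 0 to 120 minute profiles and the tolerability conclusion are not affected. The correction is worth making because, under the device sheet, outpatients lose the only glucose measurement described for home dosing with a product that the monitoring plan itself says lowers glucose.

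**What to change.** Amend the Device Review Sheet so that each outpatient is issued a meter and strips at visit 1, after the training that the Methods already plan. The outpatient records the pre-dose and 30-minute readings on each between-visit day and returns the meter and log at visit 2. The data sheet in Appendix 2 already has 0 and 30 minute rows with a glucose column and could serve as the log. The coordinator keeps the shared meter for inpatients. In the Methods, state whether the check surrounds the morning dose, the afternoon dose or both.

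The cost is at most 23 meters (fewer, since some participants are inpatients), 6 to 10 glucose strips per outpatient at one checked dose a day or 12 to 20 at two, and a short amendment. It adds no visit, staff or finger stick beyond those in the Methods. Some self-recorded readings will be missing or mis-logged.

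Dropping the between-visit checks for outpatients would also remove the contradiction, at the price of having no glucose measurement during home dosing. If outpatients have already completed the study, the text should still be corrected, and the report should say which of them had between-visit readings.
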